Clinical Investigational Plan (CIP) Information	
Protocol Title	The EMPrintTM Ablate and RESect Study in Patients with Metastatic Lung Tumors (EMPRESS)
CIP Number	COVEMPR0437
Version Date	05 March 2018
Revision	Version 3.0
Sponsor Representative	[name] RN, BSN Director Clinical Research

Summary of Changes to CIP			
Rev.	Section	Description of Change	Reason for Change
2.0	3.2.2 Procedure Planning Application	Change from investigational device to FDA cleared device with specific indications for use	FDA cleared the procedure planning application
	5.3.1 Histological Analysis	Change number and type of samples read at core lab; change from 2 to 3 categories to evaluate complete ablation: 1) Complete Ablation, 2) Delayed Necrosis, 3) Incomplete Ablation	Consistent with final Histology Charter; add subgroup for delayed necrosis
	5.5.1 Inclusion Criteria	Add inclusion of primary LC; reduce tumor-free parenchyma requirement between the pleura and tumor from ≥ 2 cm to ≥ 1 cm	Investigator feedback
	5.5.2 Pre-procedure Exclusion Criteria	Exclude only GOLD Stage IV instead of GOLD Stage III and IV; delete specific test parameters for uncontrollable	Inclusion of primary LC population more likely to have GOLD Stage III disease and be surgical

		coagulopathy	candidates; investigator feedback
	5.7.5 Microwave Ablation Planning and Procedure	Addition of 4 th CT after antenna is removed	Capture acute pneumothorax and/or bleeding events attributed to ablation procedure
	5.7.6 Planned Surgical Resection	Change acceptable time delay until surgical procedure definition from “day after ablation” to 36 hours after ablation. Change definition of protocol deviation to surgery performed beyond 36 hours after ablation,	Clarify definition for protocol deviation
	5.7.8 Sample Preparation for Histological Analysis	Addition of dye and fixation methods	Consistent with final Histology Charter
	7.2 Risks associated with Additional Radiation Exposure from Study-related CT imaging	Updated dose of radiation exposure	Addition of 4 th CT
	8.10 Adverse Event Recording and Reporting	Specify which adverse events will be collected	Consistent with final Safety Plan
	11.1 Statement of Compliance	Statement following ISO GCP	clarity
	13.0 Monitoring	Statement following ISO GCP	clarity
3.0	CIP Information	Removed Sponsor Representative Location	Redaction of personal and proprietary information for CT.gov Results Posting to comply with Final Rule

2.0 Acronyms and Definitions

Term	Definition
ADE	Adverse Device Effect; Adverse event related to the use of an investigational medical device, including adverse events resulting from insufficient or inadequate instructions for use, deployment, implantation, installation, or operation, or any malfunction of the investigational medical device, as well as any event resulting from use error or from intentional misuse of the investigational medical device.
AE	Adverse event; Any untoward medical occurrence, unintended disease or injury, or untoward clinical signs (including abnormal laboratory findings) in subjects, users or other persons, whether or not related to the investigational device. This includes events related to the investigational device or the comparator and procedures involved.
ASADE	Anticipated serious adverse device effect; an effect which by its nature, incidence, severity, or outcome has been identified in the risk analysis report (R0042262).
CIP	clinical investigational plan
CRF	Case report form
CT	computed tomography
Device deficiency	Inadequacy of a medical device related to its identity, quality, durability, reliability, safety, or performance, such as malfunction, misuse or use error and inadequate labeling.
EC	Ethics committee (see IEC)
eCRF	Electronic case report form
H&E	Hematoxylin and eosin stain routinely used to evaluate the structural integrity of cells
IEC	Institutional ethics committee (see EC)
IFU	Instructions for Use; a manual or document accompanying a technical device that describes the directions by which the device should be used, applied, etc.
Investigative Site	An approved, participating study center/institution
Investigator	Either a principal, coordinating or sub-investigator, unless otherwise specified
IRB	Institutional Review Board
ITT	Intention to treat
MITT	Modified intention to treat
MWA	microwave ablation
NADH	β -nicotinamide adenine dinucleotide, reduced; assay used to determine cell viability

OR	Operating Room
----	----------------

RDC	Remote data capture; internet-based data entry system used to enter and store study data points
RTP	remote temperature probe
SADE	Serious adverse device effect; adverse device effect that has resulted in any of the consequences characteristic of a serious adverse event
SAE	Serious adverse event; an adverse event that 
 a) led to death, b) led to serious deterioration in the health of the subject, that either resulted in 
 1) a life-threatening illness or injury, or 2) a permanent impairment of a body structure or a body function, or 3) in-patient or prolonged hospitalization, or 4) medical or surgical intervention to prevent life-threatening illness or injury or permanent impairment to a body structure or a body function, c) led to fetal distress, fetal death or a congenital abnormality or birth defect 
NOTE: Planned hospitalization for a pre-existing condition, or a procedure required by the clinical investigational plan, without serious deterioration in health, is not considered a serious adverse event.

TEAE	Treatment-emergent adverse event; any event not present prior to the initiation of the treatments or any event already present that worsens in either intensity or frequency following exposure to the treatments.
USADE	Unanticipated serious adverse device effect; serious adverse device effect which by its nature, incidence, severity or outcome has not been identified in the current version of the risk analysis report.

3.1 Introduction

3.2 Background/Justification of Investigation

Following CT-guided ablation of the tumor, a CT image will be performed to evaluate dose response. The ablation zone will then be resected as part of the standard surgical procedure and the tissue specimen will be examined using histology to determine the completeness of tumor ablation.

3.3 Report of Prior Investigations

The Covidien Emprint™ Ablation System under study in the current clinical investigational plan (CIP) was cleared by the U.S. FDA (K133821) in April 2014 and CE Mark was obtained in March 2014.

4.0 Identification and Description of Devices

4.1 Device Description

Devices that will be used in this study are the Emprint™ Ablation System and Accessories (K133821). Refer to the Emprint™ System IFU's and User's Guide for component descriptions. Additionally, the Emprint™ Procedure Planning Application, version 1.1 will be used to plan ablation dosing. Refer to the Emprint™ Procedure Planning Application, version 1.1 User's Guide for a description of the device.

Please reference the Instructions for Use for the Emprint™ Ablation System and Accessories. The Emprint™ Ablation Generator, the Reusable Cable, the Pump, and the Cart are provided non-sterile and are not used in the sterile field. These four components are reusable. Cleaning instructions for these components are provided in the Emprint™ Ablation System User's Guide, Reusable Cable Instructions for Use, and the Emprint™ Cart Instructions for Use.

The Emprint™ Percutaneous Antenna is provided sterile, is single use, and is intended to be used within the sterile field.

4.2 Indications

The Emprint™ Ablation System is intended for use in percutaneous, laparoscopic, and intraoperative coagulation (ablation) of soft tissue, including partial or complete ablation of non-resectable liver tumors. The System is not intended for use in cardiac procedures.

The Emprint™ Procedure Planning Application is a stand-alone software product that allows physicians to visualize and compare CT image data. The display, annotation, and volume rendering of medical images aids in the intervention planning for video-assisted thoracoscopic surgery (VATS) and ablation procedures using the Emprint™ Ablation System. The software is not intended for diagnosis.

4.3 Warnings

The following uses of MWA have not been studied:

- Pregnant patients: Microwave ablation procedures are not recommended for pregnant patients. Potential risks to the patient and/or fetus have not been established.
- Patients with implantable pacemakers and other electronic implants. Microwave ablation procedures are not recommended for patients with cardiac pacemakers or other implanted electronic devices. Potential risks have not been evaluated.

4.4 Identification and Dosage

Once all internal Covidien requirements are met, the Emprint™ Ablation System, the Emprint™ Percutaneous antennas, the reusable cable, ablation pump, and ablation cart and isolation transformer, will be shipped to each site. Additionally, a laptop loaded with the Emprint™

Procedure Planning Application, version 1.1, will be sent to each site prior to the study. Each site will document the quantity, lot number and/or serial number of each piece of equipment upon receipt.

5.1 Study Design

5.2 Overview

This will be a post market prospective, non-randomized, single-arm, multicenter study, designed to demonstrate dose response of the Emprint™ Ablation System using a percutaneous approach in patients with metastatic or primary lung tumors.

Up to 30 subjects who are scheduled for resection of metastatic or primary lung tumor(s) will be enrolled. Ablations will be carried out using a percutaneous approach at a dose (power and time setting) selected during procedure planning. NOTE: The procedure planning application will be used as an adjunct planning tool. While the physician prescribes the dose, the Emprint™ Procedure Planning Application overlays the 3-dimensional predicted ablation zone on the patient CT images, facilitating visualization of the predicted ablation zone relative to the target tumor. Once the ablation procedure is complete, the scheduled surgical tumor resection will be performed. Up to 10 study sites in the United States and Europe will participate in this trial.

5.3 Primary Effectiveness Endpoint: Dose Response

[figure not shown]
The primary endpoint of this study is dose response. Dose response will be assessed by comparing actual ablation zone size and volume to predicted ablation zone size and volume prescribed by the physician using the Emprint™ Procedure Planning Application, version 1.1. Dose response will be measured for each ablation zone using CT imaging immediately post ablation and prior to the surgical resection.

All measurements used to determine dose response will be measured and reported by an independent core imaging lab. To assess dose response, the following measurements will be taken:

Predicted Ablation Zone:

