5.2.1 Predicted Ablation Zone Size

- The width (X), height (Y), and depth (Z) of the ablation zone, as depicted in the planning application annotation (via snapshot) will be measured and reported. All measurements will be taken from the planes depicted in **Figure 3.1**.
- Ablation zone volume as calculated by the planning application, captured in the snapshot.
- Volume is calculated using the ellipsoidal approximation where A is width and is assumed to be axially symmetric, and B is height.

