5.7.5 Microwave Ablation

In accordance with inclusion criteria, target tumors ≤ 3.0 cm in maximum axial diameter resulting from either distant primary cancers or primary lung cancers are eligible to be considered target tumors for the study analysis. Ablation dosing will be dependent on physician prescription based on target tumor size plus a minimum of a 0.5 cm margin, established during the ablation planning phase.

Ablation Planning and Procedure

If the pre-operative CT was taken greater than 30 days prior to the date of the procedure, a low-dose CT image will be taken prior to initiating the ablation procedure to confirm the tumor size and location prior to ablation planning. The interventional radiologist or thoracic surgeon will use the pre-procedure CT in the Emprint™ Procedure Planning Application to initiate ablation planning. Investigators will first launch the lung ablation planning application on the planning application laptop. They will next import the baseline CT from a USB drive onto the planning laptop and verify the quality of the CT image as assessed by the planning application. Once the investigator has located the tumor, he or she will add a virtual target to the target tumor and take a snapshot of the final target annotation. The investigator will then add an ablation zone that encompasses the target tumor with a minimum margin of 0.5 cm. They will select the appropriate antenna length from the dropdown menu, adjust the antenna trajectory to reflect desired insertion vector and mark the antenna insertion depth. The investigator will then view the planned ablation zone and antenna trajectory in all available planes for three dimensional confirmation of placement, and make any necessary adjustments to the ablation zone and/or antenna trajectory to ensure a safe and effective planned ablation. Finally, the investigator will take a snapshot of the final plan to capture predicted ablation zone measurements and calculated predicted ablation volume.

Patients will be positioned on the CT table (*e.g.*, supine, prone, or lateral) according to the location of the tumor, to achieve the shortest accessible path to the tumor in the position most tolerable to the patient. The microwave antenna will be applied percutaneously through a skin nick and will be advanced under CT guidance. Once final placement of the antenna has been achieved, a CT image will be taken to verify final placement.

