6.5.1 Primary Endpoint

The primary endpoint is dose response immediately post-procedure (for each target tumor) and is defined as the percentage change from the predicted outcome to the actual outcome. The percentage change (calculated as $100*(A-P)/P$) will be calculated for each target tumor, where P=predicted and A=actual. The percentage change will be calculated for each tumor for the following measurements:

- Ablation zone width (X)
- Ablation zone height (Y)
- Ablation zone depth (Z)
- Ablation zone volume
- Ablation zone shape

For each of the above measurements, the percentage change for all tumors will be summarized. Summary will also be done by tumor type.

The predicted values will come from the Procedure Planning Application and the actual values will come from the CT imaging.

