## 7.9. Evaluation of Objectives

### 7.9.1. Primary Endpoint

The primary endpoint is dose response immediately post-procedure and prior to surgical resection and is defined as the percentage change from the predicted outcome to the actual outcome.

The predicted values are from the PLAN CRF:

- Predicted ablation zone width (X)
- Predicted ablation zone height (Y)
- Predicted ablation zone depth (Z)
- Predicted ablation zone volume
- Calculated ablation zone volume (calculated from predicted X, Y, and Z value)

$$\text{Calculated Ablation Zone Volume} = \frac{4 * 3.14}{3} * \frac{\text{Predicted Ablation Zone Width} * \text{Height} * \text{Depth}}{8}$$

- The predicted ablation zone shape is the calculated ratio of predicted ablation zone width (X) and ablation zone height (Y)

$$\text{Predicted Ablation Zone Shape} = \frac{\text{Predicted Ablation Zone Width}}{\text{Predicted Ablation Zone Height}}$$

The actual values are from the IMAGE CRF:

- Width (X)
- Height (Y)
- Depth (Z)
- Ablation zone volume

$$\text{Calculated Ablation Zone Volume} = \frac{4 * 3.14}{3} * \frac{\text{Actual Ablation Zone Width} * \text{Height} * \text{Depth}}{8}$$

- Ablation zone shape

$$\text{Ablation Zone Shape} = \frac{\text{Ablation Zone width}}{\text{Ablation Zone height}}$$

This document is electronically controlled. Printed copies are considered uncontrolled.

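### The core lab is assigned both the predicted and the actual zone dimensions, and neither document masks the actual reading to the prediction; the SAP's source for the predicted values also needs reconciling with the protocol

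*Protocol*

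**What the plan says.** **Who measures.** The protocol's section on the primary effectiveness endpoint states: "All measurements used to determine dose response will be measured and reported by an independent core imaging lab". The lists that follow cover the predicted zone and then the actual zone.

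**Predicted zone.** Under Predicted Ablation Zone Size (5.2.1), width, height and depth "as depicted in the planning application annotation (via snapshot) will be measured and reported". Predicted volume is not a reader measurement: "Ablation zone volume as calculated by the planning application, captured in the snapshot". Section 5.7.5 places the snapshot in the planning phase, before ablation, and gives it to the investigator: "the investigator will take a snapshot of the final plan to capture predicted ablation zone measurements and calculated predicted ablation volume".

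**Actual zone.** Section 5.2.3 has the three dimensions measured on the post-ablation CT, with the smallest diameter taken as width when the zone is not circular. Volume comes from a volumetric software package. Section 5.7.5 specifies no intravenous contrast and says the scan used for dose response, the third of four, is taken before the antenna is withdrawn.

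**Sources named for the analysis.** Protocol 6.5.1: "The predicted values will come from the Procedure Planning Application and the actual values will come from the CT imaging". SAP 7.9.1: "The predicted values are from the PLAN CRF" and "The actual values are from the IMAGE CRF". Neither document says who completes either form.

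**Not stated in either document.** There is no masking of the reader to the plan, no reading order, no lock of the actual measurements and no second read.

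**The concern.** The endpoint is closeness of A to P. Whoever places the border on the post-ablation scan determines A. If that person has already seen P, doubtful borders may be settled towards it, and the planning application then looks more accurate than it is.

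Nothing else in the plan would expose this. The study has a single arm, SAP 7.5 rules out any test on the primary endpoint, and there is no success threshold. The mean, standard deviation, median and range of the percentage change are the whole primary result, so a bias in A goes directly into the reported figure.

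The second issue is the source of P, which is the denominator of every percentage change. The protocol has the core lab measure predicted width, height and depth from the snapshot. The SAP takes them from a form whose author is not named. A reader of the final report could not tell which values were used.

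**Working it through.** The documents give no reader-error or bias figure to reproduce. The check compares the texts and then illustrates sensitivity with assumed inputs.

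**Side by side**

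| Item | Protocol | SAP |
|---|---|---|
| Predicted X, Y, Z | Core lab, from the planning snapshot (primary endpoint section, 5.2.1); from the planning application, reader not named (6.5.1) | PLAN CRF, author not named (7.9.1) |
| Predicted volume | Calculated by the application (5.2.1) | PLAN CRF (7.9.1) |
| Actual X, Y, Z | Core lab, third CT (5.2.3, 5.7.5) | IMAGE CRF, author not named (7.9.1) |
| Actual volume | Volumetric software (5.2.3) | IMAGE CRF; an X, Y, Z formula is also shown (7.9.1) |
| Masking or reading order | Not stated | Not stated |

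Site completion of the PLAN CRF is plausible. The investigator does the planning, the protocol's assessments table puts planning under the procedure day, and SAP 7.7.1 lists the predicted dimensions beside planned power, time and approach. It remains an inference. The items that 5.7.5 sends to the core lab are CT images and reconstructions, and the snapshot is not among them. The route by which the lab would obtain the snapshot is therefore also unstated.

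**Illustration 1: sensitivity to the traced border.** From the protocol: the planned margin is at least 0.5 cm. Assumed: a 2.0 cm tumour and A close to P. The predicted width is then 20 + 2 × 5 = 30 mm.

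- Border moved 1 mm on each side: 2/30 = 6.7 percentage points of width error.
- The same shift in all three dimensions, with volume calculated from X·Y·Z: (32/30)³ − 1 = +21.4%, or (28/30)³ − 1 = −18.7%.
- A 1 mm error in the recorded P: 1/30 = 3.3%, so about 3.3 points of width error.

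**Illustration 2: a reader drawn towards the plan.** Let e be the true percentage error in each dimension and f the assumed fraction of the way the reader moves towards P. The recorded dimension error is e(1 − f). The recorded X·Y·Z volume error is (1 + e(1 − f)/100)³ − 1.

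| True e | f = 0 | f = 0.25 | f = 0.50 |
|---|---|---|---|
| −5% | −14.3% | −10.8% | −7.3% |
| −10% | −27.1% | −20.9% | −14.3% |
| −20% | −48.8% | −38.6% | −27.1% |

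(Cells are volume errors.) With a common f, every dimension error is multiplied by (1 − f), so the mean and the standard deviation shrink together. The result looks both less biased and more precise.

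The volume figures apply to a volume calculated from X, Y and Z. They need not apply to volume from the software package.

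**The case against.** The strongest reply is that silence does not show an unmasked reading. Reading order usually sits in an imaging charter, which is not among these documents, and the snapshot is not listed among the items sent to the lab. This stands as far as it goes: the documents leave the risk open and do not say that the reader sees the plan. But the protocol does give the lab the predicted dimensions, and being independent of the sponsor or site is not the same as being masked. If a charter covers the point, the protocol or SAP should cite it.

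A reader might go further and infer that taking P from the PLAN CRF makes the comparison non-independent, so that the trial must have either an unmasked reading or a dependent one. The documents do not support that. The predicted values are application output captured before ablation, so copying them to a form does not make the reading of A depend on P. If the site completes the form, the core-lab reader need not see the plan at all, which would make masking easier. Nor do the documents name two different assessors for P, because the SAP names a form and not a person.

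Transcription risk is also partly covered. Protocol 13.1 provides for monitoring against source records, and 13.2 for discrepancy review, queries and a new signature on changes. These controls are general and do not mention the PLAN CRF.

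Finally, the illustrations show sensitivity to where the border is placed. They do not show that readers will drift towards P or by how much. That is correct.

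**Conclusion.** Two gaps hold. First, the core lab is assigned the predicted dimensions and the actual zone, and nothing keeps the person reading the actual zone from seeing the prediction first. Because the reading needs judgement and the endpoint is agreement, an unmasked read could pull the error towards zero. Second, the protocol and SAP do not settle where P comes from.

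The size of the bias cannot be derived from the documents. The 6.7-point figure assumes a 30 mm predicted zone and a 1 mm border shift on each side. The volume figures also assume equal shifts in three dimensions and a volume computed from them. Sample size, power and alpha are unaffected, because the plan has no sample size calculation and no test. This is a cheap improvement to the measurement of the primary endpoint, and the study as designed can still answer its question.

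**What to change.** State in the protocol's primary endpoint section and in SAP 7.9.1:

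1. The core-lab reader measures and locks X, Y, Z and volume on the third CT without access to the planning snapshot, the PLAN CRF or the dose.
2. There is one source for the predicted values. Either the core lab reads them from the pre-ablation snapshot, opened only after the lock, or they come from the PLAN CRF, verified against that snapshot. The second option lets the plan stay away from the imaging reader altogether.
3. Who completes the PLAN and IMAGE CRFs.

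The images and the lab stay the same, and nothing changes for patients. The cost is a lock step in the reading workflow, a few sentences in the two documents, and possibly a less favourable error figure. Masking will not be perfect, because the lab also measures the tumour and could guess a rough target from its size and the minimum margin. It does remove the exact predicted values from view.
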